16-May-2011

**LipaCreon® Granules 300 mg Sachet
& LipaCreon® Capsules 150 mg**

Protocol for Special Investigation (All cases)

- Special Investigation (All cases) of LipaCreon in patients with pancreatic exocrine insufficiency due to Cystic Fibrosis -**

Protocol No. : P12-893

LipaCreon® Granules 300 mg Sachet & LipaCreon® Capsules 150 mg
Protocol for Special Investigation (All cases)

- Special Investigation (All cases) of LipaCreon in patients with pancreatic exocrine insufficiency due to Cystic Fibrosis -

1. Objective of registry

The registry aims at collecting the information related to the safety and efficacy in the pancreatic exocrine insufficiency (PEI) patients due to cystic fibrosis (CF) receiving the treatment with LipaCreon in order to obtain the information for the effective and safe use of LipaCreon.

2. Planned number of cases for the registry and justification

Planned number of cases: All the cases

Justification:

The number of enrolled patients in the domestic clinical studies was few, and prompt collection of sufficient information is necessary. And the nationwide CF patient number who was reported during the whole year of 2004, was 13, and the total patients population of CF patient for 10 years from 1995 was 38*. The number of CF patients in Japan is extremely few. From this background, the target of the study is all the cases treated with LipaCreon.

*) The Research Result relating to the intractable pancreatic diseases conducted by MHLW Scientific Research Subsidiary Intractable Disease Research Enterprises during 2005 to 2007: 205-215, 2008

3. Target patients of registry

Patients with PEI attributable to primary disease of CF.

<Indications>

Replacement of pancreatic digestive enzymes in PEI

<Precautions for use related to indications>

Administer LipaCreon to patients with having symptoms of steatorrhea or other symptomatology due to PEI because of underlying diseases of chronic pancreatitis (CP) during non-compensatory period, pancreatectomy (PY) and pancreatic CF, etc.

<Contraindication>

- (1) Patients with a history of hypersensitivity to the ingredient of LipaCreon.
- (2) Patients with a history of hypersensitivity to porcine protein.

4. Dosage & administration method

Usually, 600 mg/meal of LipaCreon should be administered t.i.d. orally, immediately after meal.

In addition, the dose should be adjusted as needed based on patient's condition.

If dosage increase from usual daily dosage (1800mg) is to be done during the observation period or follow-up period, perform measurement of nutritious assessment items and monitor the symptoms relating to pancreatic exocrine insufficiency before the dosage increase. (Please refer 8. Items of registry (7) and (8))

[Precautions related to dosage and administration method]

In regarding to the adjustment of dosage and administration, age, weight, volume of meal, dietary and frequency of meal, etc. should be considered.

[Important Precaution]

In overseas, there were reports of stenosis of ileocecal area and colon (fibrosing colonopathy) in CF patients who have been administrated with high dosage of pancreatin products. So, careful observation should be provided and if any abnormality or change of abdominal symptom was found, appropriate action should be taken. Especially for patients with PEI due to CF, careful observation is necessary if patient is administered over 150 mg (equivalent to 1/2 sachet or one capsule) per kg body weight per day of Pancrelipase.

5. Number of planned institutions for registry by department

The registry will take place in departments of pediatric, internal medicine, digestive organs, and gastroenterology, etc. The number of the planned institutions is unknown because the contract will be signed after confirming the CF patient's availability in that institution.

6. Method of registry

(1) Request/Contract of the Registry

The target medical institutions are where LipaCreon is to be adapted/delivered and any CF patient is under or planning to be provided treatment. Medical Representative in charge of each medical institution explains to the doctors and relating people in charge, the purpose, target subjects and method of this registry sufficiently. In case the acceptance for the participation to this registry was obtained, he/she takes actions for the contract. The contract is to be signed between the head of medical institution and the sponsor in writing.

(2) Selection of target patients and registration

- 1) Prospective registry method is employed. It is an all cases registry.
- 2) Doctor in charge of this registry registers the patient is under or planning to be provided treatment by LipaCreon, by sending facsimile the registration form to the registration center. The registration form should include following items :
 - ① Patient ID No., ② Sex, ③ Date of birth or age,
 - ④ Inpatient/outpatient classification,
 - ⑤ Start date of administration,
- 3) In case any patient who had been administered with LipaCreon were enrolled, the information before the enrollment is to be collected as much as possible if it is required in the registry items.

(3) Observation Period

The observation period for a case is at least 52 weeks from the start of administration of LipaCreon. Even if the administration period exceeded 52 weeks, the assessment is to be done at the time of 52nd weeks. After 52nd week, administration status, concomitant use drug status, nutritious assessment items, symptoms relating to pancreatic excretion insufficiency and adverse events should be described in the Follow-up Case Report Form, and it should be submitted to the sponsor company.

(4) Description and submission of the Case Report Form

In this Registry, the Case Report Form is consisted of seven report brochures. After each whole follow-up period per case is completed, follow-up items should be fulfilled on all the registered cases (incl. discontinued cases). After all items were fulfilled, final confirmation date

should be written, signature should be done, and seal should be done before submission.

The Case Report Form (1): From the first administration date to 52nd week

The Case Report Form (2) – (7): After 52nd administration, one CRF per year

(5) Discontinued cases

In this Registry, the cases which the administration was discontinued during the observation period, or which follow-up became impossible due to patient's visit stopped, or other reasons, will be handled as "discontinued cases". For these discontinued cases, stopped date, reason of stopping, assessment done until the discontinuation should be written in the forms.

7. Planned registry period

Planned registry period: From the release of Lipa Creon to 31st March 2018

Case registration period: From the release of Lipa Creon to 31st March 2017

Observation period: For 52 weeks from the start of administration of LipaCreon. Even if the administration period exceeded 52 weeks, the assessment is to be done at the time of 52nd weeks.

Follow-up period: After the 52nd week, administration status, concomitant use drug status, nutritious assessment items, symptoms relating to pancreatic excretion insufficiency and adverse events should be described in the Follow-up Case Report Form annually, and it should be submitted to the company.

After administration of LipaCreon started, the information will be collected until the end of March 2018. First 52 weeks from the start will be observation period and 53 weeks and onwards will be follow-up period.

8. Survey items

(1) Items required for specifying the patient:

Patient ID No.

(2) Patient background:

Sex, presence or absence of pregnancy/breast feeding (female only), date of birth or age, inpatient/outpatient classification, start date of administration, concomitant diseases (hepatic, renal or respiratory disorders, other), history of disease, history of allergy, prior treatment drug (digestive enzyme product)

(3) Administration status of LipaCreon:

Daily dose, administration period, drug regimen compliance, the reason for a change in dose

(4) Administration status of concomitant drugs:

[Other digestive enzyme products]:

Presence or absence of treatment with other digestive enzyme product, drug name, daily dose, administration period

[Other concomitant drugs]:

When additional information is required at the onset of adverse event, etc., the following information is investigated:

Presence or absence of information for the concomitant drugs, drug name, administration route, reason for use, daily dose, administration period

(5) Adverse events

All the undesirable or unintended diseases, or their symptoms, signs or abnormal changes in laboratory test values, etc. that have occurred in the patients administered LipaCreon are handled as the adverse events regardless of the causal relation to LipaCreon. The adverse events whose causal relation to LipaCreon is not deniable are handled as adverse reactions.

Concerning the adverse events that occur from the start to the completion of administration of LipaCreon, the following items are investigated. In principle, the course of adverse event is observed until the event is judged by the physician in charge of registry to cause no clinical problem.

Diseases, symptoms, signs or abnormal changes in laboratory test values which were attributed to the cystic fibrosis, will not be regarded as adverse event, but as the events attributed to cystic fibrosis.(please refer to [(6) Events attributed to cystic fibrosis])

1) Presence or absence of adverse event 2) Name of adverse event

3) Date of onset 4) Seriousness 5) Administration of LipaCreon
6) Measure taken about the adverse event 7) Date of outcome (or outcome confirmation date) 8) Outcome 9) Causal relation to LipaCreon 10) Factors other than LipaCreon 11) Symptoms and history of adverse event 12) Laboratory test results related to the adverse event 13) Comment on the adverse event

(6) Events attributed to cystic fibrosis

Information regarding below items should be collected on the diseases, symptoms, signs or abnormal changes in laboratory test values which were attributed to the cystic fibrosis occurred after administration of LipaCreon.

- 1) Presence or absence of event attributed to cystic fibrosis
- 2) Name of event
- 3) Date of onset 4) Measure taken about the event
- 5) Date of outcome (or outcome confirmation date)
- 6) Outcome

(7) Nutrition assessment items

The following nutrition assessment items are determined before the start and after 4, 8 and 24 weeks from the start of administration of LipaCreon, at the end of observation period or at the time of discontinuation during observation period, and per year or at the end of follow-up period or at the time of discontinuation during follow-up period.

If the dosage increase from usual dosage (1800mg/day) is to be done during the observation period or follow-up period, perform assessment before the dosage increase.

- BMI (Height, body weight)
- Serum total protein
- Albumin
- Total cholesterol
- Triglyceride
- Hemoglobin

(8) Symptoms relating to pancreatic exocrine insufficiency

Following symptoms should be monitored at the timing before the start of administration, 4th, 8th, 24th week after administration started, and completion/discontinuation of follow-up during the observation period,

and per year or at the end of follow-up period or at the time of discontinuation during follow-up period. If the dosage increase from usual dosage (1800mg/day) is to be done during the observation period or follow-up period, those symptoms should be monitored before the increase will take place.

- Steatorrhea
- Frequency of defecation
- Diarrhea
- Bad odor of feces
- Appetite loss
- Abdominal distention

(9) Overall improvement rating

The overall improvement is assessed in the following 4 grades after 24 weeks from the start of administration of LipaCreon, and at the end of observation period at 52nd week or at the time of discontinuation.

Effective, unchanged, aggravation, unassessable

(10) Discontinuation

When the administration is discontinued during the observation period, or when follow-up became impossible due to patient's visit stopped, or other reasons, the date of discontinuation and the reason for discontinuation is stated in the CRFs.

(11) Case of pregnancy

The information related to pregnancy is separately investigated in the pregnant case and the case whose pregnancy is found during the observation period at the point the pregnancy is known and after the birth of baby.

Survey schedule

Survey items	At the start of administration	Time point					
		During observation period				During Follow-up period	
		After 4 weeks	After 8 weeks	After 24 weeks	After 52 weeks or at the discontinuation	Per year	At the end of Follow-up Period (Mar. '18) or at the discontinuation
Registration	○						
Patient background	○						
Administration status of LipaCreon	○			○		○	○
Administration status of concomitant drug	○			○		○	○
Nutrition assessment items*	○	○	○	○	○	○	○
Symptoms relating to pancreatic exocrine insufficiency *	○	○	○	○	○	○	○
Overall improvement rating				○	○		
Reason for discontinuation					At the time of discontinuation ○		At the time of discontinuation ○
Adverse events	Investigation from the start of administration and throughout the observation period						
Events attributed to cystic fibrosis	Investigation from the start of administration and throughout the observation period						

* : If dosage increase from usual daily dosage (1800mg) is to be done during the observation period or follow-up period, perform measurement of nutritious assessment items and monitor the symptoms relating to pancreatic exocrine insufficiency before the dosage increase.

9. Timing, items and methods of analysis

(1) Timing of analysis

After 3 or 4 years from start of registry, the interim analysis is to be done.

And at the end of registry, the final analysis is to be done.

(2) Matters related to case formation

- Number of registered cases and number of cases from which the CRF is collected
- Number of cases accepted for safety and efficacy analysis
- Number of cases excluded from analysis and the reason for exclusion

(3) Matters related to safety

- Adverse reaction onset status
- Factors considered to have influence on the safety (The incidence of ADRs by patient background)
- Adverse event and serious adverse event

(4) Matters related to effectiveness

- Changes in nutrition assessment items
- Overall improvement rating
- Factors considered to have influence on the efficacy (The list related to efficacy by patient background)

10. System organized for the conduct of registry

Abbott Japan Co., Ltd.

- Post-marketing Studies Manager : [name]
Post Marketing Study Group, Medical, Pharma Products Group

11. Name and address of the person who consigned this job, and the scope of consigned job

Person who consigned this job

(1) Address: [name]

Name: [name], Post-marketing Studies Manager
Eisai Co., Ltd.

Scope of consigned job: Conduct of special investigation (request for the conduct, contract conclusion, collection of registration cards and re-survey, collection of CRFs and re-survey, collection of adverse event information, etc.)

(2) Address: [name]
Name: EPS Co., Ltd.
Scope of consigned job: Case registration job, data management job, statistics analysis job)

12. Medical Professional

(1) Address: [name]
Affiliation: Department of Gastroenterology, Tohoku University School of Medicine
Name: [name] (Professor)
Scope of work: Medical advice for this investigation.

(2) Address: [name]
Affiliation: Department of Respiratory disease, Omori Red Cross Hospital
Name: [name]
(Department director of respiratory tract medicine)
Scope of work: Medical advice for this investigation.

13. Other necessary matters

(1) Amendment of registry plan

When a new finding is obtained during this registry period, the necessity or not of the protocol amendment is investigated, and the amendment is made as required. The necessity or not of the protocol amendment is also investigated when the approval on a partial change in the dosage & administration or indication & effect (excluding the case when a new re-evaluation period is designated), etc. is granted, and the amendment is made as required.

(2) Measure taken when any problem or doubt arises

The conduct of new special investigation or post-marketing clinical study is investigated in the following cases so as to detect or confirm these factors or to verify the assumption, etc. obtained as a result of investigation.

- 1) When critical safety concern such as the onset, etc. of unknown & serious adverse reaction is suggested.
- 2) When a definite increase in the incidence of adverse reaction is observed.
- 3) When any problem is found in the safety and efficacy in comparison with the results of study conducted up to the time of approval.

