4.5.1.1. Occurrence of events associated with cystic fibrosis of the pancreas

For patients included in the safety analysis, a list of reported events associated with cystic fibrosis of the pancreas will be prepared (Table 5.1.1).

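### Events attributed to cystic fibrosis are taken out of the adverse events and recorded without seriousness or causality, so they cannot be counted as SAEs or ADRs

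*Protocol*

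**What the plan says.** Protocol 8(5) opens with a broad definition: undesirable or unintended occurrences in treated patients "are handled as the adverse events regardless of the causal relation to LipaCreon". Adverse reactions are a subset: "The adverse events whose causal relation to LipaCreon is not deniable are handled as adverse reactions". The same item then makes an exception. Diseases, symptoms, signs and laboratory changes attributed to CF "will not be regarded as adverse event, but as the events attributed to cystic fibrosis".

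The two kinds of event are recorded differently. The 8(5) list for adverse events has 13 items, including "3) Date of onset 4) Seriousness 5) Administration of LipaCreon" and "9) Causal relation to LipaCreon 10) Factors other than LipaCreon". The 8(6) list for CF events has six: presence, name, then "3) Date of onset 4) Measure taken about the event", then outcome date and outcome.

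SAP 2.2 (items 11 to 14) defines adverse events as what stands in the adverse event column of the case report form, and derives ADRs and SAEs from those. For CF events, SAP 4.5.1.1 says that "a list of reported events associated with cystic fibrosis of the pancreas will be prepared" (Table 5.1.1). Table 5.2.1.1 adds a present/absent flag per patient.

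The protocol also names a bowel risk of this drug class. Under Important Precaution in section 4, it says that overseas "there were reports of stenosis of ileocecal area and colon (fibrosing colonopathy) in CF patients" given high doses, and asks for careful observation of abdominal symptoms.

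**The concern.** Adverse events are first defined without regard to cause, and a group of them is then removed by a judgement about cause. The survey has a single arm and no blinding. The protocol gives no rule for making the attribution when the cause is mixed or uncertain, and plans no review of it. Once an event is filed under CF, the items needed to reclassify it are not collected.

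Elsewhere the plan resolves doubt towards the drug. A relation that cannot be denied makes an adverse reaction (Protocol 8(5)), an undeterminable relation counts as related (SAP 2.2, item 12), and serious events judged unrelated are still shown, in brackets, in Attached Form 2-2 (SAP 4.6.1.2). Attribution to CF bypasses all three.

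At stake is how far the safety rates depend on one unblinded attribution. Two of the triggers for further investigation in Protocol 13(2), an unknown serious adverse reaction and a definite rise in adverse reaction incidence, rest on data that CF-filed events never enter.

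**Working it through.** The survey takes all cases and states no target number or expected event rate, so there is no planned figure to reproduce. The check is a trace of definitions, followed by an illustration of size.

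**Step 1. Items collected (Protocol 8(5) and 8(6))**

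| Item | Adverse event | CF event |
|---|---|---|
| Presence, name, onset | yes | yes |
| Measure taken, outcome date, outcome | yes | yes |
| Seriousness | yes | no |
| Action on LipaCreon | yes | no |
| Causal relation, other factors | yes | no |
| Symptoms and history, laboratory results, comment | yes | no |

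**Step 2. Route into the counts (SAP 2.2)**

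- Item 11: an adverse event must stand in the adverse event column. A CF event is by definition not an adverse event.
- Item 13: an ADR is an adverse event assessed as related. A CF event fails the first condition and has no causality item.
- Item 14: an SAE is an adverse event with recorded causality and with seriousness marked serious. A CF event fails all three conditions.

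A CF event therefore adds zero to each numerator by construction, however serious it is. The same serious event, kept as an adverse event and judged unrelated, would appear in brackets in Attached Form 2-2.

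**Step 3. Outputs (SAP 5.2 and 6)**

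Periodic safety reports contain Attached Forms 2 and 2-2 only, which are ADR and SAE tables. Tables 5.1.1 and 5.2.1.1 to 5.2.1.3 are marked for re-examination only. Table 5.2.1.3 is headed as adverse event records, but its columns (treatment of the event, outcome date, outcome, and no seriousness or causality) resemble the CF-event items. It may be meant for CF events; the SAP does not say so.

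**Step 4. Illustration of size**

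Inputs: the share of events misfiled is not given, and neither is N. Protocol section 2 gives two national patient counts, 13 (for 2004) and 38 (ten years from 1995). They are used here only as assumed values of N.

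Patient-based rate = patients with at least one event / N (SAP 3.4 and 4.2.1.1). If one patient's only counted event is misfiled, the rate falls by 1/N:

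- N = 38: 1/38 = 2.6 percentage points
- N = 13: 1/13 = 7.7 percentage points

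If that patient has another counted event, the overall patient rate does not change.

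Second illustration: let p be the assumed probability that a patient has an ADR, and m the assumed share of such patients whose ADRs are all filed under CF. The probability that at least one patient is counted is 1 − (1 − p(1 − m))^N. With p = 5%:

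| m | Expected rate | N = 38 | N = 13 |
|---|---|---|---|
| 0 | 5.0% | 0.858 | 0.487 |
| 0.5 | 2.5% | 0.618 | 0.280 |
| 1 | 0% | 0 | 0 |

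Both p and m are assumptions. The table shows sensitivity and does not estimate a bias.

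**The case against.** Separating disease events from drug events is a reasonable aim in an uncontrolled survey, and four arguments limit the point.

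1. Mixed-cause events need not be lost. Protocol 8(5) lists factors other than LipaCreon among the adverse event items, and SAP 4.2.1.5 offers the primary disease as one such factor. A physician can keep the event as an adverse event and name CF as a contributor. This stands, and it makes the loss possible rather than certain. No sentence tells the physician to do so.

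2. A reader might infer from SAP 4.5.1.1 that CF events are only line-listed, with no counts. The SAP does not support that. Its title for Table 2.1.1.1 also speaks of a list, yet SAP 4.2.1.1 defines that table as patients, percentages and events by SOC and PT. Table 5.1.1 may already hold counts; its content is not specified.

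3. A physician who attributes an event to CF would often judge it unrelated to LipaCreon anyway, so a causality item may change few ADR counts. This has force. It applies less to SAEs, which are counted whether related or not.

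4. A reader might infer that drug-related bowel events will disappear from the survey. The documents do not show this. The precaution in Protocol section 4 directs attention to abdominal changes, and diarrhea, abdominal distention, appetite loss and stool frequency are recorded at scheduled visits whatever their cause (Protocol 8(8)) and analysed for change (SAP 4.3.3.1). CF events also keep their name, dates, measure taken and outcome. That an abdominal sign could be attributed to CF is plausible, since several such signs are listed as symptoms of the treated condition, but how often this happens is unknown.

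The case report form itself (attachment (d)) is not reproduced in the protocol. The point rests on the protocol's item lists.

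**Conclusion.** The point stands as a structural gap with an inexpensive remedy. A serious event filed under CF cannot be counted as an SAE or ADR and cannot reach the periodic forms. As an event it is reported only in the CF outputs at re-examination, without the items needed to reclassify it.

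The documents do not establish that the safety rates are biased downward, because they give no misfiling rate. Nor does every misfiled event lower incidence by 2.6 or 7.7 points. Those figures hold only when the event is the patient's sole counted one, and for assumed values of N that are national counts, not this survey's safety set.

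**What to change.** - **Protocol 8(6):** add seriousness and causal relation to LipaCreon to the items for CF events.
- **Protocol 8(5):** state that an event whose relation to LipaCreon cannot be denied is recorded as an adverse event even if CF may contribute.
- **SAP:** repeat Table 2.1.1.1 (patients, percentage of the safety set, and events, by SOC, PT and seriousness) with adverse events and CF events combined. Present it as a supplement beside the main table, which stays as it is. State what Table 5.1.1 contains and whether Table 5.2.1.3 covers CF events.

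If the form can no longer change, add the combined SOC/PT table without seriousness. It would still show how far the overall rates depend on attribution.

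The cost is a small form change, one further table, and MedDRA coding of CF events if it is not already planned. The supplementary table will show higher rates that include disease events, and should be labelled accordingly.

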Patient number lists will be prepared for the following: Patients with adverse drug reactions; patients with adverse drug reactions whose outcome is "not resolved," "with sequelae," "fatal," or "unknown;" patients who have adverse drug reactions after the completion of treatment; pediatric (aged <15 years) patients with adverse drug reactions; pregnant patients with adverse drug reactions (those who are pregnant during the duration of treatment with Lipacreon); patients with adverse drug reactions who have hepatic impairment; patients with adverse drug reactions who have renal impairment; and patients with adverse drug reactions who have respiratory disease (Table 2.1.5.2).

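### The Survey schedule ends both event rows at 52 weeks, against the protocol text for adverse events, and events attributed to cystic fibrosis have no named collection route after that

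*Protocol*

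**What the plan says.** **Schedule.** In the Survey schedule at the end of Protocol section 8, the rows for adverse events and for events attributed to CF carry one and the same entry: "Investigation from the start of administration and throughout the observation period". The schedule has separate columns for the follow-up period, and its footnote on dose increases names both periods when both are meant.

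**Where the observation period ends.** Protocol section 7: "First 52 weeks from the start will be observation period and 53 weeks and onwards will be follow-up period". Section 6(3) is looser ("The observation period for a case is at least 52 weeks from the start of administration of LipaCreon"), but it too moves to the follow-up form after the 52nd week.

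**Adverse events after Week 52.** Section 6(3) says that "symptoms relating to pancreatic excretion insufficiency and adverse events should be described in the Follow-up Case Report Form". Section 7 repeats the list and makes it annual. Section 8(5) sets its window without reference to 52 weeks: "Concerning the adverse events that occur from the start to the completion of administration of LipaCreon, the following items are investigated".

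**CF events after Week 52.** Section 8(6) asks for CF-attributed events that occur after LipaCreon has been given and states no end. The lists of follow-up form contents in 6(3) and 7 name administration status, concomitant drugs, nutrition items, symptoms and adverse events, but not CF events. Section 8(5) keeps CF-attributed events out of the adverse-event category.

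**SAP.** Section 4.2.1.2 tabulates adverse events and adverse drug reactions by time of onset up to Day 2400. CF events are listed without a time limit (section 4.5.1.1, Table 5.1.1) and shown per patient as present or absent (section 4.5.2.1, Table 5.2.1.1, item 14).

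**The concern.** The protocol gives a site two different instructions on late events. A site that fills in forms from the schedule would stop recording both kinds of event at Week 52. A site that follows sections 6(3) and 7 would go on recording adverse events, but would find no mention of CF events in the follow-up form contents.

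The split matters for this product. The protocol's Important Precaution concerns bowel stenosis (fibrosing colonopathy) in CF patients on high doses and asks for attention to abdominal changes. Whether an abdominal event is an adverse event or a CF event depends on attribution. After Week 52 that attribution also decides whether the event has a named place among the form contents.

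The population is very small: Protocol section 2 cites 38 CF patients in Japan over ten years. A few unrecorded late events could change the picture, and no analysis can recover them. Because the SAP's patient listing offers only present or absent for CF events, an event that nobody was asked to report could appear there as absent.

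**Working it through.** The plan gives no figure to reproduce. The check is a comparison of passages, followed by a count of the time affected.

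**1. Passages side by side**

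| Source | Adverse events after Week 52 | CF events after Week 52 |
|---|---|---|
| Survey schedule row | Not included | Not included |
| 6(3), follow-up form contents | Required | Not named |
| 7, follow-up form contents | Required, annually | Not named |
| 8(5) | Required to completion of administration | Excluded from adverse events |
| 8(6) | Not applicable | No end point stated |
| 7, general sentence | Information collected to end of March 2018 | Same; no item named |

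For adverse events, three passages require collection and one row contradicts them. For CF events, two general statements reach past Week 52. The only explicit time limit stops at Week 52, and no follow-up form item is named.

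**2. SAP onset categories.** Section 4.2.1.2 has 13 categories, with upper limits 28, 56, 112, 168, 224, 280, 364, 728, 1092, 1456, 1820, 2184 and 2400 days. Six lie wholly after Day 364. If every site followed the schedule row literally, those six would be empty.

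**3. Time exposed.** Inputs: survey period 30 August 2011 to 31 March 2018 (SAP 1.2); registration to 31 March 2017 (Protocol 7); one year = 364 days (SAP 3.5).

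- Longest possible time: 30 August 2011 to 31 March 2018, inclusive = 2406 days, of which 2406 − 364 = 2042 (85%) fall after Day 364.
- Shortest possible time, for a start on 31 March 2017 = 366 days, with almost nothing after Day 364.
- Even entry (assumed): mean = (366 + 2406)/2 = 1386 days. Share after Week 52 = (1386 − 364)/1386 = 73.7%.
- Constant stopping at proportion q per year (assumed): λ = −ln(1 − q)/364. Expected time for a patient with potential time T is (1 − e^(−λT))/λ, averaged over T = 366 to 2406. Time within Week 52 is (1 − e^(−364λ))/λ.

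| q per year | Mean days in total | Mean days to Week 52 | Share after Week 52 |
|---|---|---|---|
| 0% | 1386 | 364 | 73.7% |
| 5% | 1238.9 | 354.8 | 71.4% |
| 30% | 712.1 | 306.2 | 57.0% |

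**The case against.** The strongest reply is that the protocol does require late collection and that one table row is not the plan.

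- **Adverse events.** A reader might infer from the schedule that adverse-event collection stops at 52 weeks. The documents do not support that: 6(3), 7 and 8(5) require it, and Case Report Forms (2) to (7) exist for the later years. This part of the reply stands in full. What remains is a contradiction with the schedule.
- **CF events.** A reader might also infer that nothing requires late CF events. That goes too far. Section 8(6) has no end point, and section 7 says information is collected until the end of March 2018. But neither sentence names a form or item, and both conflict with the schedule row.
- **The form itself.** The Case Report Form is an attachment that is not among the documents, so it may have a field for CF events. SAP Table 5.2.1.3 sits in the CF section and has a column for the separate volume and items close to those in 8(6). This makes such a field possible, but the table is titled as adverse events and proves nothing.
- **Partial capture.** Diarrhea, steatorrhea and abdominal distention are recorded yearly in follow-up, and worsening of CF is a listed reason for discontinuation. So a late bowel event need not vanish entirely. These items do not replace an event record with onset, measure taken and outcome.
- **Late counts in the SAP.** The onset categories apply to adverse events and adverse drug reactions. CF events are only listed, so a count of late CF events is not a planned output. The risk of misreading comes from the present/absent entry.
- **Events after treatment.** The SAP has an action category for events that develop after discontinuation (4.2.1.3) and lists "patients who have adverse drug reactions after the completion of treatment" (4.2.1.5). A reader might see a contradiction with 8(5). There is none: these outputs can hold events that happen to be reported outside the required window. The counts are simply not systematic.

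**Conclusion.** The point holds as an inconsistency in collection instructions, with different weight for the two kinds of event. For adverse events the plan has no gap, but the schedule contradicts sections 6(3), 7 and 8(5) and could lead a site to under-report. For CF events the intention to collect beyond Week 52 can be read from 8(6) and 7, but no named route carries it out. A site following the schedule and the form lists would not report them, and the SAP listing could then show absence.

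About 74% of potential patient-time lies after Week 52 under assumed even entry and no stopping, and 57% to 71% under assumed stopping of 30% to 5% per year. A reader might take this as the share of safety data lost. It is only the time over which the instructions disagree or are silent; for adverse events the required loss is nil. The conclusion on CF events rests on the protocol's lists of form contents, because the form cannot be checked. The schedule was read from a PDF, so the span of the merged cell is uncertain, but its words name the observation period only.

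The correction should be made, because it is cheap and late events that are not collected cannot be recovered by analysis.

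**What to change.** 1. In the Survey schedule, change the entry in both event rows to: throughout the observation and follow-up periods.
2. In Protocol 6(3) and 7, add events attributed to CF to the contents of the Follow-up Case Report Form, and make sure that the form has the field.
3. Minor: in SAP 4.2.1.3 and 4.2.1.5, label the outputs for events after the end of treatment as not systematically collected, because Protocol 8(5) requires collection only to completion of administration.

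The cost is protocol wording, one field on the follow-up form, a label on the SAP outputs and a small reporting burden for sites.
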